7 DISCONTINUATION OF STUDY INTERVENTION AND PARTICIPANT DISCONTINUATION/WITHDRAWAL

7.1 Discontinuation of Study Intervention

It may be necessary for a participant to permanently discontinue (definitive discontinuation) study intervention. If study intervention is permanently discontinued, the participant should remain in the study, ie, continue to participate in scheduled study visits and evaluations.

Note that discontinuation from study intervention is NOT the same thing as a withdrawal from the study. For procedures in the case of withdrawal from the study, see Section 7.2.

At each visit, participants will be instructed to contact the investigator immediately, if rash or skin reaction has developed. If maculopapular rash grade 1, 2, or 3 has developed, participant must be permanently discontinued from the study intervention and AZ medical staff should be informed.

- Grade 1: Macules/papules covering < 10% Body Surface Area with or without symptoms (eg, pruritus, burning, tightness).

- Grade 2: Macules/papules covering 10 - 30% Body Surface Area, with or without symptoms (eg, pruritus, burning, tightness); limiting Instrumental ADL (refer to preparing meals, shopping for groceries or clothes, using the telephone, managing money, etc); rash covering > 30% Body Surface Area with or without mild symptoms.
- Grade 3: Macules/papules covering > 30% Body Surface Area, with moderate or severe symptoms; limiting Self-care ADL (refer to bathing, dressing and undressing, feeding self, using the toilet, taking medications, and not bedridden).

If the participant develops a rash or skin reaction that is not considered a maculopapular rash, but is a generalised rash/skin reaction or is considered to be an SAE, the participant must be permanently discontinued from the study intervention and AZ medical staff should be informed.

For further information and skin reaction evaluation guidance, see Appendix B 5.

Study participants also may be discontinued from study intervention in the following situations:

- Participant decision. The participant is at any time free to discontinue treatment, without prejudice to further treatment.
- Adverse Event or other safety reasons as judged by the Investigator and/or sponsor where continued treatment may put the participant at undue risk.
- Development of uncontrolled and clinical significant **CCI** as judged by the Investigator.
- Severe non-compliance with the CSP.
- Pregnancy

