7.1.1 Temporary Discontinuation

Every attempt should be made to maintain participants on the study intervention during the course of the study. If the study intervention has been interrupted, it should be re-introduced as soon as, in the opinion of the Investigator, the participant is able to re-start study treatment. Note related to AEoSI skin reactions (including maculopapular rash): In the occurrence of maculopapular rash CTCAE Grade 1, 2, or 3, or any other generalised rash/skin reaction or serious rash/skin reaction, study intervention should be permanently discontinued. At each visit, participants will be instructed to stop the study intervention and contact the investigator immediately if rash or skin reaction has developed. After the participant has been seen by the study doctor or designee and the skin reaction is not considered a maculopapular rash CTCAE

Grade 1, 2, or 3, or any other generalised rash/skin reaction or serious rash/skin reaction, the study treatment can be restarted.

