7.1.2 Rechallenge

Participants who have temporarily discontinued study intervention can resume treatment as soon as, in the opinion of the Investigator, the participant is able to re-start study treatment and the participant wishes to resume. No minimum time period is necessary before treatment can resume.

If a participant develops maculopapular rash CTCAE Grades 1, 2, or 3 or any other generalised rash/skin reaction or serious rash/skin reaction, study intervention should be permanently discontinued.

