8.2.5 Skin Reactions, Including Maculopapular Rash

Skin reactions, including maculopapular rash, will be considered AEs of special interest in this study. To ensure that data are collected systematically, any skin reaction will be recorded on a special eCRF page. All skin reactions should be recorded in the eCRF as an AE or SAE. If the rash is considered maculopapular, it will be evaluated using CTCAE grades 1-3 for rash maculopapular; if not considered maculopapular, severity will be captured as

mild/moderate/severe, along with data element components generally used for CTCAE grading of other skin reactions, given that CTCAE grading is specific to the particular type of skin lesion. For all rashes, various aspects of the rash will be documented, including start/end date, morphology of lesions (maculopapular vs other morphologies), body surface area impacted, anatomical site(s), symptoms, signs, effect on participant (including ADL impacted), concomitant medications, medication administered, and specific rash diagnosis, if available. Photos (overview and detailed) should be taken.

Please refer to Appendix B 5 for further guidance in rash assessment and reporting.

At all visits, participants will be instructed to contact the investigator immediately if rash or skin reaction has developed at any time point during the study. Participants will be recommended to make an acceptable quality self-photo of skin affected with rash/skin reaction.

If any study participant develops a confirmed generalised maculopapular rash CTCAE grade 1-3, throat tightness or angioedema at any time during the study, the investigator should immediately stop the study drug and arrange for the participant to receive the appropriate medical treatment relevant to this situation.

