- Only half the dose is taken because the study participant feels that he/she is feeling better when not taking the whole dose
- Someone who is not enrolled in the study intentionally takes the drug

B 5 Guide to skin reaction assessment

This Appendix describes the process to be followed to appropriately identify, assess and report cases of skin reactions. Skin reactions, including maculopapular rash, will be considered AEs of special interest in this study. To ensure that data are collected systematically, any skin reaction will be recorded on a special eCRF page. All skin reactions should be recorded and reported as AEs or SAEs.

If the rash is considered maculopapular, it will be evaluated using CTCAE grades 1-3 for rash maculopapular; if not considered maculopapular, severity will be captured as mild/moderate/severe, along with data element components generally used for CTCAE grading of other skin reactions, given that CTCAE grading is specific to the particular type of skin lesion. For all rashes, various aspects of the rash will be documented, including start/end date, morphology of lesions (maculopapular vs other morphologies), body surface area impacted, anatomical site(s), symptoms, signs, effect on participant (including ADL impacted), concomitant medications, medication administered, and specific rash diagnosis, if available.

If maculopapular rash Grade 1, 2, or 3 has developed, participant must be permanently discontinued from IP, and AZ medical staff should be informed.

If the participant develops a rash or skin reaction that is not considered a maculopapular rash, the participant must permanently discontinue if the rash/skin reaction is considered an SAE or is a generalised rash/skin reaction. AstraZeneca medical staff should be informed.

At all visits, participants will be instructed to contact the investigator immediately if rash has developed at any time point during the study. Participants will be recommended to make an acceptable quality self-photo of skin affected with rash.

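### Section 8.2.5 stops study drug for throat tightness or angioedema but does not make the stop permanent, so non-serious localised angioedema and throat tightness without rash can be restarted on investigator judgement

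*Protocol*

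**What the plan says.** Protocol Section 8.2.5 puts three triggers in one sentence. If a participant develops a confirmed generalised maculopapular rash of CTCAE grade 1 to 3, "throat tightness or angioedema at any time during the study, the investigator should immediately stop the study drug" and arrange suitable treatment. The sentence does not say whether the stop is temporary or permanent.

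Permanence is set elsewhere. Section 7.1 makes it compulsory for maculopapular rash of grade 1, 2 or 3. A reaction that is not maculopapular is treated the same way if it is not limited in extent or seriousness: "but is a generalised rash/skin reaction or is considered to be an SAE, the participant must be permanently discontinued from the study intervention". Section 7.1.2 repeats this for maculopapular rash or "any other generalised rash/skin reaction or serious rash/skin reaction, study intervention should be permanently discontinued". Appendix B 5 says of non-maculopapular reactions that "the participant must permanently discontinue if the rash/skin reaction is considered an SAE or is a generalised rash/skin reaction". Section 7.1.1 carries the same list. None of these texts names angioedema or throat tightness.

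Restart is covered in two sections. Under Section 7.1.1, if drug has been interrupted, "it should be re-introduced as soon as, in the opinion of the Investigator, the participant is able to re-start study treatment". For skin reactions the same section adds that once the study doctor or designee has seen the participant, and the reaction is not a maculopapular rash of grade 1 to 3 "or any other generalised rash/skin reaction or serious rash/skin reaction, the study treatment can be restarted". Section 7.1.2 requires the investigator's opinion that the participant is able and the participant's wish to resume, and states: "No minimum time period is necessary before treatment can resume". Section 6.6 allows no dose modification.

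**The concern.** The sponsor judged throat tightness and angioedema important enough to stop drug at once, in the same sentence as the drug's identified rash risk. The rule for what happens next is written only for the rash. Wherever the protocol means a permanent stop for skin reactions, it says so in terms; here it does not. Two sites could reasonably read Section 8.2.5 differently, one as ending treatment and one as an interruption to be reversed when the participant recovers.

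What is at stake is participant safety. A participant could be re-exposed at the full assigned dose after a possible hypersensitivity event, on a decision taken by an investigator who does not know whether the participant is on active drug. No estimate or test in the SAP depends on it.

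**Working it through.** No figure is involved. The check takes each form of the two events and asks which rule reaches it.

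1. **Serious or generalised angioedema, classed as a skin reaction.** Reached by Section 7.1 and Appendix B 5, so the stop is permanent. Appendix B 2 makes this group large. It gives angioedema needing intravenous hydrocortisone as an example of an important medical event, and says such events should ordinarily be treated as serious.

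2. **Throat tightness together with a maculopapular, generalised or serious rash.** Reached through the rash, so the stop is permanent.

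3. **Non-serious localised angioedema.** Not maculopapular, not generalised, not serious: no permanent-stop text applies. If it is classed as a skin reaction, the restart sentence in Section 7.1.1 allows treatment to resume after the study-doctor review. If it is not so classed, the general re-introduction sentence in 7.1.1 applies. Restart is open on either reading.

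4. **Throat tightness without rash.** This is not a rash or skin reaction, so the permanent-stop rule does not expressly reach it, whatever its seriousness. The general provisions of 7.1.1 and 7.1.2 apply.

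For the third and fourth forms, the remaining controls are:

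- **Section 7.1, adverse-event clause:** the investigator and/or sponsor may discontinue a participant when continued treatment would carry undue risk. This permits a permanent stop without requiring one.
- **Section 7.1.1:** review by the study doctor or designee before restart, if the event is classed as a skin reaction.
- **Section 7.1.2:** the participant must wish to resume.
- **Section 8, opening text:** immediate safety concerns should be discussed with the sponsor to decide whether the participant continues or discontinues. Discussion is directed; its outcome is left open.
- **Section 8.2.5:** an extra clinic visit with full examination and safety bloods, for skin reactions.
- **Appendix B 3:** a remark that the sponsor would not normally support re-challenge. It sits in the guide to causality, not among the discontinuation rules.

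These are real controls, and some are worded as directions. None says that drug stays stopped unless another cause is found, and the 7.1.1 sentence that governs interruptions points towards re-introduction.

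**The case against.** The strongest reply is that the acute protection is already there (an immediate stop and medical treatment) and that what follows is supervised. The sponsor is to be consulted on exactly this decision, a doctor sees skin reactions before restart, and nothing directs re-exposure while an event is unresolved, because every restart provision depends on the investigator judging the participant able. This stands, and it makes the gap smaller. It does not supply a default.

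It can also be said that the stop in Section 8.2.5 is meant to be permanent, since its first trigger is permanent elsewhere. That is possible, but it is not written for the other two triggers, and the sections that govern permanence omit them.

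Three stronger readings are tempting and are not supported:

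- **That the protocol contradicts its own entry rule.** Exclusion criterion 5, in both parts, bars people with a history of drug hypersensitivity, naming angioedema without a severity threshold. The same criterion names rash and urticaria equally, yet Section 7.1.1 openly lets a localised, non-serious, non-maculopapular rash restart. Entry that is stricter than on-study discontinuation is the protocol's general design. The criterion also concerns reactions attributed to a drug, whereas on-study angioedema may have another cause.
- **That it is inconsistent to stop permanently for a Grade 1 maculopapular rash, which includes "Macules/papules covering < 10% Body Surface Area with or without symptoms", but not for mild angioedema.** Maculopapular rash is an observed signal of this drug (Sections 2.3.1 and 4.3). A stricter rule for a known signal is a defensible choice.
- **That restart is uncontrolled or may be immediate.** The absence of a fixed waiting period does not mean that drug may be given back before the investigator is satisfied.

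**Conclusion.** The point holds in a limited form. As written, non-serious localised angioedema and throat tightness without rash can be restarted at full dose on judgement, and no provision makes permanent discontinuation the default. This is a worthwhile, low-cost safety clarification, not a fault in the trial's inference.

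Its size cannot be given as a number. The visible text reports no case of either event on AZD4831 and gives no rate. Much angioedema will be classed as serious and so already covered. No endpoint or analysis changes.

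The conclusion rests on two assumptions: that a stop not declared permanent counts as an interruption under Section 7.1.1, and that no text outside the visible documents, such as site training or the Investigator's Brochure, already settles the matter.

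**What to change.** Add to Protocol Section 7.1, after the paragraph on reactions that are not maculopapular, a sentence to this effect:

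> If a participant develops angioedema, or throat tightness suspected to be a hypersensitivity reaction, whether or not serious and with or without rash, study intervention must be permanently discontinued and AZ medical staff informed, unless the investigator, in agreement with the Study Physician, documents another cause before any restart.

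Cross-reference it from Section 8.2.5 (after the stop sentence), Section 7.1.1 (the re-introduction and restart sentences), Section 7.1.2 (the sentence on waiting time) and Appendix B 5.

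The cost is one sentence and four cross-references. No new procedure is needed, and the Study Physician role already exists. Judgement remains, but the default changes and a restart requires agreement and a written reason. The downside is that a few participants may stop drug for an event it did not cause; under Section 7.1 they remain in the study and are followed up.

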8.2.6 Infection

Infections will be considered AE of special interest in this study. Local laboratory testing for microorganisms per local guidelines is requested for serious infections (those that meet SAE criteria) and results documented.

8.3 Adverse Events and Serious Adverse Events

The PI is responsible for ensuring that all staff involved in the study are familiar with the content of this section.

The definitions of an AE or SAE can be found in Appendix B.

Adverse events will be reported by the participant (or, when appropriate, by a caregiver, surrogate, or the participant's legally authorised representative).

The investigator and any designees are responsible for detecting, documenting, and recording events that meet the definition of an AE.

8.3.1 Time Period and Frequency for Collecting AE and SAE Information

Adverse events will be collected from the time of the first dose throughout the treatment period and including the follow-up period (final follow up is Visit 12 for Part A and Visit 8 for Part B). The only exception is related to the pre-dose orthostatic test at Visit 3: if orthostatic hypotension is confirmed, it should be reported as an AE, and symptoms related to the measurement of orthostatic vitals if present should also be reported as an AE.

SAEs will be recorded from the time of signing of the informed consent form.

If the investigator becomes aware of an SAE with a suspected causal relationship to the investigational medicinal product that occurs after the end of the clinical study in a participant treated by him or her, the investigator shall, without undue delay, report the SAE to the sponsor.

8.3.2 Follow-up of AEs and SAEs

Any AEs that are unresolved at the participant's last AE assessment in the study are followed up by the investigator for as long as medically indicated, but without further recording in the eCRF. AstraZeneca retains the right to request additional information for any participant with ongoing AE(s)/SAE(s) at the end of the study, if judged necessary.

Adverse event variables

The following variables will be collected for each AE:

- AE (verbatim)
- The date and time when the AE started and stopped
- Maximum intensity
- Maximum CTCAE grade for rash maculopapular
- Whether the AE is serious or not
- Investigator causality rating against the Investigational Product(s) (yes or no)
- Action taken with regard to Investigational Product(s)
- AE caused participant's withdrawal from study (yes or no)
- Outcome

In addition, the following variables will be collected for SAEs:

- Date AE met criteria for SAE
- Date investigator became aware of SAE
- AE is serious due to
- Date of hospitalisation
- Date of discharge
- In case of fatality:
 - Probable cause of death
 - Date of death
 - Autopsy performed
- Causality assessment in relation to study procedure(s)
- Causality assessment to other medication

8.3.3 Causality Collection

The investigator should assess causal relationship between Investigational Product and each AE, and answer ‘yes’ or ‘no’ to the question ‘Do you consider that there is a reasonable possibility that the event may have been caused by the investigational product?’

For SAEs, causal relationship should also be assessed for other medication and study procedures. Note that for SAEs that could be associated with any study procedure the causal relationship is implied as ‘yes’.

A guide to the interpretation of the causality question is found in Appendix B to the Clinical Study Protocol.

8.3.4 Adverse Events Based on Signs and Symptoms

All AEs spontaneously reported by the participant or reported in response to the open question from the study site staff: ‘Have you had any health problems since the previous visit/you were last asked?’, or revealed by observation will be collected and recorded in the eCRF. When collecting AEs, the recording of diagnoses is preferred (when possible) to recording a list of signs and symptoms. However, if a diagnosis is known and there are other signs or symptoms that are not generally part of the diagnosis, the diagnosis and each sign or symptom will be recorded separately.

8.3.5 Adverse Events Based on Examinations and Tests

The results from the Clinical Study Protocol mandated laboratory tests and vital signs will be summarised in the CSR.

Deterioration as compared to baseline in protocol-mandated measurements should therefore only be reported as AEs if they fulfil any of the SAE criteria, are the reason for discontinuation of treatment with the investigational product or are considered to be clinically relevant as judged by the investigator (which may include but not limited to consideration as to whether treatment or non-planned visits were required or other action was taken with the study intervention, eg, dose adjustment or drug interruption).

If deterioration in a laboratory value/vital sign is associated with clinical signs and symptoms, the sign or symptom will be reported as an AE and the associated laboratory result/vital sign will be considered as additional information. Wherever possible the reporting investigator uses the clinical, rather than the laboratory term (eg, anaemia versus low haemoglobin value). In the absence of clinical signs or symptoms, clinically relevant deteriorations in non-mandated parameters should be reported as AE(s).

Any new or aggravated clinically relevant abnormal medical finding at a physical examination as compared with the baseline assessment will be reported as an AE unless unequivocally related to the disease under study.

8.3.6 Hy's Law

Cases where a participant shows elevations in liver biochemistry may require further evaluation and occurrences of AST or ALT $\geq 3 \times$ ULN together with total bilirubin $\geq 2 \times$ ULN may need to be reported as SAEs. Please refer to Appendix E for further instruction on cases of increases in liver biochemistry and evaluation of Hy's Law.

8.3.7 Reporting of Serious Adverse Events

All SAEs have to be reported, whether or not considered causally related to the investigational product, or to the study procedure(s). All SAEs will be recorded in the eCRF.

If any SAE occurs in the course of the study, investigators or other site personnel will inform the appropriate AZ representatives within one day ie, immediately but **no later than 24 hours** of when he or she becomes aware of it.

The designated AZ representative will work with the investigator to ensure that all the necessary information is provided to the AZ Patient Safety data entry site **within one calendar day** of initial receipt for fatal and life-threatening events **and within 5 calendar days** of initial receipt for all other SAEs.

For fatal or life-threatening AEs where important or relevant information is missing, active follow-up will be undertaken immediately. Investigators or other site personnel will inform AZ representatives of any follow-up information on a previously reported SAE within one calendar day, ie, immediately but **no later than 24 hours** of when he or she becomes aware of it.

Once the investigators or other site personnel indicate an AE is serious in the EDC system, an automated email alert is sent to the designated AZ representative. If the EDC system is not available, then the investigator or other study site staff reports a SAE to the appropriate AZ representative by telephone. The AZ representative will advise the investigator/study site staff how to proceed.

For further guidance on the definition of a SAE, see Appendix B of the Clinical Study Protocol.

The reference document for definition of expectedness/listedness is the IB for the AZ drug.

